### **Aim 1b Procedure:**

Task Scenario Development and Pilot Test: Usability testing clinical scenarios will be developed by two subject matter experts ([name] and [name]). Tasks will include adding CKD to the problem list, placing lab and/or medication orders, and printing patient education handouts. We will also include a test scenario that could lead the PCP to decide not to follow the CDS recommendation and we will see if they are able to enter a justification without assistance (see “accountable justification” section below). The scenarios will be reviewed by the research team to ensure that the content, format, and presentation are representative of real expected use and address the major components of the CDS. Then we will pre-load test patients with the data necessary for these scenarios and prepare the usability test procedure (described below). The usability test will be piloted with a PCP and we will ask for feedback on the usability test process, as well as content and wording of test scenarios.

Usability Test Procedure: A usability test plan will be developed that includes details on the testing procedure, tasks, usability metrics, usability goals, and appendices containing the test scenarios, pre-test instructions, and post-test interview questions. A moderator and observer from the research team will both attend each session. First, the moderator will describe the usability test procedure using scripted pre-test instructions to ensure that all participants receive the same instruction. The participant will be informed of the goal of evaluating the CDS and that the session will be video-taped. The moderator will describe the “think-aloud” process, asking the participant to share their thought process and expectations while completing the tasks. An example of think aloud will be demonstrated. Then, the moderator will begin recording the session using Morae software. The participant will read each task aloud, attempt the task, and inform the moderator when the task is complete. The moderator will record task success or failure based on the intended outcome as described in the test plan. If a participant is having trouble completing a task, he or she will be given an assist at the moderator’s discretion. The observer will make note of assists and other usability or comprehension issues that arise. After all tasks are complete, the moderator will administer a verbal post-test interview. The moderator will ask questions like, “How did you interpret this?”, “Why did

you do X?" and "What would you change about the content of the CDS?" The moderator and observer will manually record observations during the testing session. In addition to the comments and data recorded during the session, usability metrics will be coded after the session using Morae software. Usability metrics are measurements collected to determine to what extent usability goals have been met. The metrics will include task completion success rates, time-on-task, error rates, and assists by the moderator. We will be able to compare these measurements to those gathered from subsequent tests to determine whether iterative changes to the CDS have improved the usability of the CDS. Qualitative analysis: Qualitative methods will be employed to analyze the data. The research assistant will review the video recordings to identify usability issues based on observations of the participants during the task and the participants' think-aloud comments. Video recordings will be transcribed verbatim, and subject identifiers will be removed from the transcripts. The transcripts will be organized by task and participant and then quotes will be identified that illustrate a user expectation, frustration, or misinterpretation of content or functionality.

Pilot Study: Prior to the clinical trial, a pilot study will be conducted in live clinical settings. A subgroup of PCPs will be selected and the BPAs will be turned on for approximately one month. Interaction with the BPAs will be monitored. Each time a BPA fires the research team will contact the PCP by email to gather feedback through surveys and/or interviews. Iterative refinement of BPAs may be undertaken.

**Aim 1c Procedure:**

- 1) Pre-checked, no-action default: The first nudge will be part of the CDS. We will display the CDS with certain options pre-selected. We plan to include addition of the CKD diagnosis to the problem list and addition of a patient education handout to the after-visit summary.
- 2) Pledge email to obtain commitment from PCPs to follow the CDS recommendations: As a starting point, we need to ensure that PCPs are aware of the clinical practice guidelines. At the beginning of the study, we will send an advertisement email to all PCPs in the network. In addition, as part of the intervention, we will ask PCPs to commit to following the recommendations presented to them in the BPA, or writing their rationale in the CDS if they choose not to. The PI will send an email via REDCap to intervention PCPs giving a brief overview of the CDS content. By clicking a link in the email, the intervention PCP will come to a REDCap survey asking them to type their name to pledge to consider the CDS recommendations provided in our BPAs. The control PCPs will receive a similar email without the specific details about our study and without the REDCap link.

Behavioral Science Methods Review Committee: Though the research team does include co-investigators with expertise in behavioral science methods, we have decided to convene an advisory group consisting of three experts in behavioral science as applied in interventions for both PCPs and patients. We have chosen the members of this committee based upon their familiarity with chronic disease management interventions and EHR-based interventions. We have limited the group to three members because we plan to meet on a monthly basis during the first two years of the study. This group will give advice to the research team on elements of Aim 1 and the roll-out of the clinical trial.

**Specific Aim 2 & 2a Procedures:**

**Setting:** The Brigham and Women's Primary Care Practice-Based Research Network (BWPC PBRN) is one of 155 PBRNs nationally certified by the Agency for Healthcare Research and Quality (AHRQ). The BWPC PBRN is a network of 15 practices which includes hospital-based practices, community-based practices, and community health centers affiliated with Brigham and Women's Hospital. The network includes 185 primary care physicians that care for approximately 150,000 patients.

**Subjects:** All patients over the age of 18 who have a visit with a PCP at one of the intervention practices during the 2 years preceding the study period will be eligible. We are able to utilize data from the past five years stored in the EHR to identify CKD patients with uncontrolled HTN. The first inclusion criteria will be CKD, defined as two prior eGFR 16-59 mL/min/1.73m^2 separated by 90 days, as calculated by CKD-EPI, or two prior UACR >30mg/g. The second inclusion criteria will be uncontrolled hypertension, defined as at least two SBP >140 mmHg within the 2 years preceding the study period. We will exclude all patients who are currently pregnant. The CDS will review lab data starting five years before the visit to determine whether the patient has CKD using the logic described above. If the patient has CKD, the CDS will search BP data starting one year before the visit to determine whether the patient has had at least two SBP > 140 mmHg.

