### III. SUBJECT SELECTION

**Subjects:** All patients over the age of 18 who have a visit with a PCP at one of the intervention practices during the 2 years preceding the study period will be eligible. We are able to utilize data from the past 2 years stored in the EHR to identify CKD patients with uncontrolled HTN. The first inclusion criteria will be CKD, defined as two prior eGFR  $16-59$  mL/min/1.73m $^2$  separated by 90 days, as calculated by CKD-EPI, or two prior UACR  $>30$ mg/g. The second inclusion criteria will be uncontrolled hypertension, defined as at least one SBP  $>140$  mmHg within the 2 years preceding the enrollment visit, as well as SBP  $>140$  mmHg at the enrollment visit. Our objective was to include PCPs who have a consistent panel of primary care patients. We obtained a list of currently employed physicians, physicians assistants and nurse practitioners in our primary care network of 15 practices. We excluded residents in training, as well as physicians who were only seeing urgent care and walk-in patients.

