## V. STUDY PROCEDURES

### **Aim 1, and 1a Study Procedures:**

Modify Rules for Automated Diagnosis of CKD and Uncontrolled HTN: [name] is a participant in the NKDEP Health Information Technology care plan working group. She has contributed to their efforts to new national standards for diagnosis of patients with CKD using EHR data. We will modify the rules from the MAPLE study in order to align them with this new national standard. Then, we will create rules for automated diagnosis of uncontrolled hypertension. We will implement the BPA in “silent mode” for the control arm. This means that we will identify control patients in real time according to the same inclusion criteria as intervention patients, excluding all patients who are pregnant.

Develop Rules for Evidence-based Recommendations for HTN in CKD: We will leverage past work that we have done in a study that delivered recommendations based on JNC7. An example of one of the rules is to determine whether anti-hypertensive agents have been prescribed but are not at highest potency. If so, the CDS will deliver a recommendation to increase the dosage. Or, if multiple agents have been prescribed at maximum potency, the CDS will access the patient’s refill record. If the patient has not been refilling medications on schedule, the tool will recommend a medication adherence discussion. We will also include one-click access to documentation and orders relevant for CKD. For example, a message that gives a specific diagnosis, “This patient has stage 3b CKD with unknown level of albuminuria”), as well as an actionable order, “Click here to order a urine microalbumin to creatinine ratio test.” The BPA will include a BP entry field in which a PCP can record a repeat BP reading. If the PCP enters a BP reading, it will automatically be recorded in the vital signs flowsheet and vice versa. We will include appropriate laboratory monitoring test orders. Confirmatory testing is appropriate for an abnormal urine albumin level, so we will include an order if the prior result was abnormal. We will also provide one-click access to print patient handouts. In order to minimize cognitive overload and improve self-efficacy we will only deliver three messages at one time. We will develop a ranked list to drive the choice of recommendations. For example, in patients with CKD and HTN who smoke, tobacco cessation would be the highest priority.

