## VII. RISKS AND DISCOMFORTS

There are minimal risks to physicians or patients as a result of the intervention. For clinicians, there is a risk that the decision support and other tools could have unexpected adverse consequences such as creation of more work, unfavorable workflow issues, and overdependence on technology. Although important to consider, these risks are balanced by evidence suggesting the effectiveness of computerized clinical decision support to improve the quality of patient care. For patients, the risks are those that are typically undertaken in the receipt of general medical care. That is, it is conceivable that the intervention could result in a change in management (e.g., ordering more tests, referral), but in the case of chronic kidney disease this may in fact lead to a clinical benefit. There also is the possibility of psychological risk to patients associated with being labeled as having chronic kidney disease; however, this risk is outweighed by the potential benefits associated with better evaluation and treatment of the disease. Finally, there is a risk of overtreatment of hypertension which may cause hypotension or an acute decrease in kidney function. The intervention is delivered to the primary care physician, who will weigh the risk and benefit of treatment intensification. However, this risk is expected to be low since we only recommend treatment intensification within consensus guidelines.

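### The CKD definition sets no interval between the two UACR values, so two urine samples from one short episode meet a chronic-disease rule whose label is pre-checked in the intervention arm

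*Combined protocol and SAP*

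**What the plan says.** The definition appears twice with the same structure, in III. Subject Selection and in V. Study Procedures (Specific Aim 2 & 2a Procedures, Subjects). It opens "The first inclusion criteria will be CKD, defined as two prior eGFR 16-59" and continues "separated by 90 days, as calculated by CKD-EPI, or two prior UACR >30mg/g".

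Specific Aim 2 & 2a Procedures then ties the software to this definition: "The CDS will review lab data starting five years before the visit to determine whether the patient has CKD using the logic described above". The clinical exclusion stated there is pregnancy: "We will exclude all patients who are currently pregnant".

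Aim 1c Procedure plans a no-action default in the alert that includes "addition of the CKD diagnosis to the problem list". The Aim 1 and 1a procedures say the control arm is identified in real time by the same criteria, with the alert silent. They also say "Confirmatory testing is appropriate for an abnormal urine albumin level", and offer an order for it inside the alert. Specific Aim 2b lists a documented CKD diagnosis among its process measures, although Table 1 has no row for it. Section VII names a "psychological risk to patients associated with being labeled as having chronic kidney disease".

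**The concern.** The two routes to CKD are alternatives, and only one of them contains a test of persistence. The 90 days on the eGFR side keep a short-lived fall in eGFR from being read as chronic disease. The UACR side has no counterpart, so a short-lived rise in urine albumin that is sampled twice passes.

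Two things are at stake, both in the intervention arm:

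- **Labelling.** The diagnosis is pre-selected, so it can be recorded through inaction. Section VII accepts the labelling risk because better evaluation and treatment of the disease outweigh it. That argument is weaker for a patient whose albuminuria was transient.
- **Aim 2b.** A newly recorded CKD diagnosis counts as improved care. A label resting on a transient finding would count in the same direction, and only intervention PCPs see the prompt.

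**Working it through.** No sample size, power or alpha figure is involved, and the plan states no figure to reproduce. The check is to set the two routes side by side, run the rule as written on hypothetical laboratory histories, and look for any other text that closes the gap.

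**Conditions in each route (Sections III and V)**

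| Condition | eGFR route | UACR route |
|---|---|---|
| Number of values | two | two |
| Limit on each value | 16-59 mL/min/1.73m² | >30 mg/g |
| Interval between values | 90 days | none stated |
| Condition on eGFR | the range itself | none stated |

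The interval cannot comfortably be read across both routes. It stands before the *or* and is followed by the reference to CKD-EPI, which concerns eGFR alone: "separated by 90 days, as calculated by CKD-EPI, or two prior UACR".

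**Rule as coded.** A patient qualifies if either holds within five years before the visit: (i) two eGFR values of 16-59 at least 90 days apart; (ii) two UACR values above 30, at any spacing. Reading the interval as at least 90 days is an assumption. The histories are invented to test the logic and say nothing about frequency.

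| Hypothetical history | As written | With 90 days on the UACR pair |
|---|---|---|
| eGFR 85; UACR 80 twice, 3 days apart | qualifies (UACR) | does not qualify |
| eGFR 85; UACR 80 twice, 120 days apart | qualifies (UACR) | qualifies (UACR) |
| eGFR 50 twice, 3 days apart; no UACR | does not qualify | does not qualify |

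The first and third rows show the asymmetry: the same 3-day spacing passes for urine albumin and fails for eGFR. The second row shows that the added interval keeps patients whose albuminuria persists.

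**Does other text supply the interval?**

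- The confirmatory urine order is offered inside the alert, after the patient has already qualified. It states no spacing.
- The rules are to be aligned with a national standard, but the documents do not give its content.
- The silent-mode review of 150 charts (10 in each of 15 clinics) checks whether the rules identify patients correctly. No UACR interval is written down for it to check against.
- The SBP criterion must also be met for enrolment. It restricts who enters but does not bear on whether the albuminuria is chronic.

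**Size.** Let s be the share of intervention patients who qualify only through UACR values all less than 90 days apart, t the fraction of these whose albuminuria is transient, and a the fraction for whom the pre-checked diagnosis is left in place. Mistaken labels then make up s × t × a of the arm, which cannot exceed s. The documents give none of the three, so no number follows.

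**The lower eGFR limit.** Three further histories, under the rule as written:

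| Hypothetical history | As written |
|---|---|
| eGFR 12 twice, 200 days apart; no UACR | does not qualify |
| eGFR 12 twice, 200 days apart; UACR 900 twice, 200 days apart | qualifies (UACR) |
| eGFR 30 and 25 about four years ago, now 12; no UACR | qualifies (eGFR) |

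Patients now below 16 can therefore enter by either route. The limit applies to the qualifying values and not to current eGFR.

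**The case against.** The strongest reply is that the practical effect may be small. The rule already asks for two abnormal values, so it does not contradict the remark on confirmatory testing, which sets no interval. The PCP sees the pre-checked item and can decline it; the usability scenarios in Aim 1b include deciding against a recommendation and entering a justification. Urine albumin appears to be tested sparsely: Section I reports that only 40% of the network's CKD patients had such a test, and Aim 2b treats it as an annual measure. Closely spaced pairs may therefore be uncommon. All of this stands and limits the weight of the point. None of it puts an interval into the rule.

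Three stronger readings are tempting, and the documents do not support them.

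- **A multiplier for false entry.** One could model two samples in a single episode and report how much more often they both exceed 30 than well-separated samples do. The answer depends on an assumed correlation between close samples, and it applies to the trial only if every UACR pair comes from one episode. The documents support neither assumption.
- **Patients below eGFR 16 evade an exclusion and are mislabelled.** The 16-59 range describes qualifying values in one route and is not stated as an exclusion. Persistent eGFR below 16 with albuminuria is not a false CKD label, and the eGFR route also admits patients who have since declined below 16.
- **The primary comparison is biased.** Both arms are identified by the same rule, so the gap does not select patients differently by arm.

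**Conclusion.** The point holds as a gap in the definition. As written, two UACR values above 30 mg/g at any spacing meet a chronic-disease criterion, although the plan requires 90 days of the other marker. The consequence is confined to labelling in the intervention arm and to the meaning of the Aim 2b documentation measure. The randomized SBP comparison is not biased by selection. The size is unknown and should be left unquantified until the share entering by UACR and the spacing of the pairs have been counted.

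The conclusion rests on reading the interval as belonging to eGFR only, which is the natural reading, and on the software being coded from this text, as Section V says. If the sponsor intended the 90 days to cover both tests, the wording still needs to say so. The lower eGFR limit is a separate and lesser matter: it is a question of target population, and the text leaves it open.

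**What to change.** In III. Subject Selection, in Specific Aim 2 & 2a Procedures, and in the rule shared by the live and silent alerts, require the two UACR values to be separated by the same 90 days already required of eGFR. Do this before go-live, so that both arms are identified by one rule throughout.

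During the silent-mode run, count the patients who qualify only through UACR values less than 90 days apart. That count measures both the problem and the price of the change, since these are the patients who would no longer qualify on the data then available.

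Separately, the sponsor should state whether the lower limit of 16 defines the trial population or only the eGFR route, and which eGFR value it refers to (the qualifying values or the current one). Sections III and V and the coded logic should then be reconciled.

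The cost is one added condition in a shared rule, two text edits and a somewhat smaller eligible pool.

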### IV. SUBJECT ENROLLMENT

Randomization and Enrollment: This study will utilize a matched-pair cluster randomized design with the intervention on the cluster level, and the main outcome (6 month minus baseline change in SBP) measured at the patient level. We will have 174 clusters (made up of 185 clinicians) in the study. We will match pairs of clusters with similar number of patients and prior year mean blood pressure of patients in the cluster. One cluster in each pair will be randomized to the intervention and unit one to usual care. Patients will be electronically identified and included in the study over the course of 12 months. Patients seen by PCPs during the pilot study will be excluded. Retrospective data indicates that 70% of patients have a follow-up around 6 months. Outcomes assessment will occur at 180 days (+/- 60 days). After the 12-month enrollment period ends, data collection will continue for 6 months so that those enrolled toward the end of the enrollment period will have a full 6 months to complete any interventions ordered by the PCP. A small subset of PCPs will be enrolled in a pilot study for approximately one month, as described below in study procedures Aim 1b. Clinical outcomes will be recorded and reviewed every month over the course of the trial.

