Implementation of CDS in Epic: The next step is implementation in Epic as a BPA. Each of the rules will be added to the Epic database. The BPAs appear in an area of the screen that is visible when orders are being entered. Currently, there are several cancer screening BPAs and a seasonal influenza BPA. The CDS will be moved to the Production environment in “silent mode” before the scheduled start date of the trial, where it will record when it would fire, but it will not be displayed to the user. This step will allow us to validate that the rules are accurately identifying patients and producing the correct recommendations through a chart review. We will review 10 charts of patients with CKD and uncontrolled HTN per clinic for a total of 150 charts. The CDS will be activated in the Production environment on the start date of the clinical trial in Aim 2.

Validation of Hypertension-specific Process Measures: In preparation for the clinical trial in Aim 2, we will validate three process measures. Two of the measures will reflect treatment intensification by the PCP, 1) an increase in dosage or 2) addition of a new anti-hypertensive agent. The third measure will reflect medication adherence by the patient using data from a pharmacy benefits manager. We will perform a retrospective chart review of 150 charts to calculate the sensitivity and specificity of each rule.

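### Patients enter up to 12 months after their PCP's arm goes live, yet no patient-level pre-start SBP is named as baseline or covariate in the primary analysis

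*Combined protocol and SAP*

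**What the plan says.** Section IV pairs clusters on panel size and on their patients' average BP in the previous year. Then "One cluster in each pair will be randomized to the intervention and unit one to usual care". Section V (Implementation of CDS in Epic) states: "The CDS will be activated in the Production environment on the start date of the clinical trial in Aim 2". On entry, section IV says: "Patients will be electronically identified and included in the study over the course of 12 months". Control patients are found in real time by the same rule, run silently (section V, Aim 1a).

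The BP criterion has three time windows:

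- Section III: at least one SBP above 140 "mmHg within the 2 years preceding the enrollment visit", plus SBP above 140 "mmHg at the enrollment visit".
- Section V, Specific Aim 2 & 2a, definition: at least two SBP above 140 "within the 2 years preceding the study period".
- Same paragraph, what the software does: "the CDS will search BP data starting one year before the visit", looking for at least two SBP above 140.

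Both sections also require a PCP visit "during the 2 years preceding the study period will be eligible".

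The primary outcome is the 6-month change in SBP (section IV; section VI, Table 1). Neither section says which reading is the baseline, and section VI gives no model or covariate for this outcome. The multilevel logistic model in Aim 2b is for process measures.

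**The concern.** A baseline should be free of the arm. Here the PCP is the randomised unit and the PCP's behaviour is what the trial sets out to change. An intervention PCP receives the overview email and the pledge (section V, Aim 1c) and sees alerts on other patients from the start date. If that PCP begins treating hypertension in CKD differently across the panel, a patient whose first qualifying visit comes in month 8 may already have a lower SBP. Some such patients no longer qualify. The rest enter from a lower reading, and their untreated SBP is on average higher than that of their control counterparts.

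Silent identification in the control arm removes recruiter choice. It does not make the SBP readings fed into the rule independent of arm. At stake is an SBP effect biased toward the null, in a field where section I cites an average effect of 1 mmHg for decision support in non-CKD hypertension. There is also a plain loss of precision, because several pre-start readings per patient are not used in the model.

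**Working it through.** The plan states no power, SD, ICC or target difference, so there is no figure of its own to reproduce. All results in mmHg below rest on assumed inputs.

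**1. Share of the look-back after the start.** For entry in month m, the share is m/12 of a one-year window and m/24 of a two-year window.

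| Entry month | One-year window | Two-year window |
|---|---|---|
| 0 | 0% | 0% |
| 3 | 25% | 12.5% |
| 6 | 50% | 25% |
| 9 | 75% | 37.5% |
| 12 | 100% | 50% |

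Uniform entry would give averages of 50% and 25%. First qualifying visits cluster early, however. Simulated mean entry is near month 4, or 4/12 = 33% of the one-year window (range 31 to 39%).

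**2. What spill-over does to entry and baseline.** Assumed: mean SBP 135; between/within-patient SD 12/10 or 10/14; entry if one history reading and the enrolment reading both exceed 140 (the section III rule); entry uniform over 12 months; true effect d = 3; spill-over s lowering every post-start reading taken before treatment begins. There were 2,000,000 candidate patients per arm. Differences are intervention minus control.

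| SDs | s | Entry ratio | Baseline SBP | Underlying untreated mean | Estimated change |
|---|---|---|---|---|---|
| 12/10 | 0 | 0.998 | -0.005 | +0.012 | -2.97 |
| 12/10 | 0.75 | 0.950 | -0.242 | +0.286 | -2.50 |
| 12/10 | 1.5 | 0.901 | -0.538 | +0.591 | -1.88 |
| 10/14 | 0 | 0.999 | +0.013 | 0.000 | -3.02 |
| 10/14 | 0.75 | 0.945 | -0.204 | +0.228 | -2.55 |
| 10/14 | 1.5 | 0.900 | -0.496 | +0.371 | -2.14 |

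The loss is the sum of two parts: the rise in the underlying mean and the fall in baseline. For SDs 12/10 and s = 1.5, the estimate should be -3 + 0.591 + 0.538 = -1.87, against -1.88 simulated. With s = 0 there is no distortion beyond simulation error.

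**3. What a pre-start covariate does.** Assumed: spill-over growing to 2 mmHg by month 12, d = 3, and 3 to 7 pre-start readings per patient.

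- Raw change loses about 0.4 to 0.8 mmHg. With enrolment SBP plus the pre-start mean, the loss is about 0 to 0.25.
- Under other plausible inputs (between-patient SD 10 to 15, visit SD 10 to 12, drift SD 5), raw change loses 0.3 to 0.8, adjustment for enrolment SBP alone loses 0.2 to 0.7, and adding the pre-start mean leaves 0 to 0.4.
- This fits step 2. At mean entry near month 4, the average spill-over is about 2 × 4/12 = 0.67 mmHg, close to the s = 0.75 rows, which lose 3 - 2.50 = 0.50 and 3 - 2.55 = 0.45.

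**4. Precision with no spill-over.** The pre-start mean lowers patient-level residual variance by about 13 to 26% beyond enrolment SBP alone. For example, 188 to 163 with 3 readings is 25/188 = 13%, and 191 to 152 with 7 readings is 39/191 = 20%. Less favourable inputs give as little as 8%. On the standard error, √0.87 = 0.93 and √0.74 = 0.86, so it is 7 to 14% smaller before between-PCP variance is counted.

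**5. Re-anchoring the history instead.** With 2 mmHg spill-over and raw change, the loss is about 0.3 to 0.55 mmHg with the rolling history and 0.3 to 0.45 with a history restricted to pre-start readings (simulation error about 0.05). The enrolment-visit reading still selects patients and sets the baseline, so most of the bias stays.

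**6. Scale.** 2,350/174 = 13.5 patients per cluster, and 70% follow-up leaves 1,645 patients. With 80% power, two-sided 0.05, and assumed SD 15 to 20 and ICC 0 to 0.05, the detectable difference is about 2.1 to 3.3 mmHg.

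**The case against.** The strongest reply is that a post-start date is not itself a bias. The visible alert fires on the same criteria that define entry, so an individual patient is not directly exposed before entering. The only nudge outside the alert is the email and pledge, which concern recommendations shown in the alert, and control PCPs get a similar email without the study details. A panel-wide spill-over of 2 mmHg is twice the 1 mmHg average effect cited in section I. This stands: the bias is conditional, and its size is unknown.

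A reader might infer that pre-start SBP is ignored altogether. It is not. Section IV matches clusters on it, and the Aim 2 definition sets a window wholly before the study period. What is missing is a patient-level pre-start SBP in the primary analysis.

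A reader might also infer that half of each look-back is contaminated, or that patients are exposed for up to 12 months before baseline. The 50% needs uniform entry, and the 12 months is exposure of the PCP. That randomisation precedes enrolment is itself inferred, from activation on the start date, matching on previous-year data and silent control alerts.

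Finally, the variance gain depends on assumed SDs and reading counts, and is measured against an enrolment-SBP model that the plan does not state. That is fair, but it bears on the size of the gain rather than on its direction.

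**Conclusion.** The point holds in a limited form. Under the rolling rules, qualifying SBP can be read after the arm is live, and an enrolment-visit baseline always is. Section VI names no patient-level safeguard. If spill-over exists, the bias runs toward the null; at an assumed 2 mmHg by month 12 it is a few tenths of a mmHg, modest beside the detectable difference but not beside a 1 mmHg effect. If there is none, this route produces no bias. The documents do not show that the primary result will be biased.

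The case for acting does not rest on spill-over, because the covariate improves precision either way. The figures depend on the assumed SDs, 3 to 7 pre-start readings per patient, and the section III type of entry rule. Any effect of the alert's repeat-BP field on the baseline reading is a separate matter and is not counted here.

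**What to change.** - In section VI, analyse 6-month SBP with two covariates: enrolment SBP, and each patient's mean of all SBP readings dated before the trial start. Use a missing indicator for patients without a pre-start reading. They should be few, since eligibility already requires a visit in the preceding 2 years.
- For patients of pilot PCPs, use only readings dated before the pilot. Those PCPs saw live alerts for about a month and then join the intervention arm.
- Report qualifying and enrolled counts per cluster by arm. A shortfall in the intervention arm would be a visible sign of spill-over.
- Reconcile the BP windows in section III and in the Aim 2 procedures.
- Keep restriction of the history criteria to pre-start readings as, at most, a sensitivity analysis. Alone it removes only part of the bias, and it drops patients whose PCPs were alerted about them, which sits badly with a pragmatic trial.

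The cost is a small extra EHR extraction and a few sentences in section VI. Patient care and the alert itself do not change.
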